### **5.5 Efficacy Analysis**

#### **5.5.1 Primary Efficacy Analysis**

The FAS and the PPS will be used for the analysis of the primary efficacy analysis.

The primary endpoint is the proportion of patients who experience the first US within the first 6 months (until Day 182) after randomisation (failure rate). First US within the first 6 month, deaths before the first US and patients without evaluable assessment of the primary endpoint will be counted as treatment failures. The first occurring event will be used for this analysis e.g. if a patient experiences an US and dies later, this patient will be included as a patient with an US. If a patient experienced a re-stroke, the patient will be counted as a withdrawal with the date of re-stroke as ‘Date of withdrawal’.

To show that ESL is different to placebo, the primary null hypothesis

$$H_0: p_{ESL} \geq p_{placebo}$$

will be tested against the alternative hypothesis

$$H_1: p_{ESL} < p_{placebo}$$

where  $p_{ESL}$  and  $p_{placebo}$  denote the proportions of patients with the first US within 6 months after randomisation in ESL and placebo patients, respectively.

The primary hypotheses will be assessed in the FAS by means of a chi-square test with continuity correction on the significance level of 5% (two-sided, which corresponds to the significance level of

2.5% one-sided). The Odds Ratio for Placebo vs. ESL and the corresponding 95% score CI will be provided. The Risk Difference (RD) of failing between Placebo and ESL with corresponding 95% continuity-corrected Newcombe Confidence Interval (CI) for the risk difference Placebo – ESL will be calculated. Additionally, the p-value of Fisher's exact test will be provided.

For this purpose, the following SAS code will be used:

**Note: Data should be sorted by descending treatment group (first “ESL” then “Placebo”) and by treatment failures (first “Failure” then “Non-failure”).**

```
PROC FREQ DATA = <dataset> order=data;
  TABLE <Treatment group> * < Treatment Failure>
    /CHISQ RISKDIFF (CL =Newcombe (Corrected)) OR(CL =SCORE) ALPHA=0.05;
RUN;

PROC FREQ DATA = <dataset> order=data;
  tables <Treatment group> * < Treatment Failure>/ fisher;
run;
```

The following statistical outputs will be created:

Table 15.2.1.1.1 Analysis of Treatment Failure Rate within 6 Months after Randomisation – Full Analysis Set

Table 15.2.1.1.2 Analysis of Treatment Failure Rate within 6 Months after Randomisation – Per-Protocol Set

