Number and percentage of failures (overall, US, death, early withdrawal, missing) and non-failures 6 months after randomisation will be tabulated, including degrees of freedom (DF), value and p-value for chi-square test, p-value for Fisher's exact test, RD of failing between ESL and Placebo with corresponding 95% continuity-corrected Newcombe CI as well as ESL vs. PlaceboOR with 95% score confidence interval.

Listing 16.2.3.1 Seizure Screening Questionnaire – Enrolled Set

Seizure screening questionnaire data will be listed.

Listing 16.2.3.2 Seizure Information after the Primary Stroke Occurrence – Enrolled Set

Seizure information after the primary stroke occurrence will be listed.

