### **5.5.1.1 Sensitivity Analyses**

For the primary analysis, patients withdrawing early during the trial will be considered as non-seizure free (treatment failure). This replacement strategy is defined under the assumption that it cannot be excluded that “missingness” is related to treatment failure and thus not at random. In order to assess the effect of missing data, the following sensitivity analyses will be performed:

The primary analysis will be repeated by imputing the missing values (patient withdrew from study before primary endpoint was reached) in both groups (ESL and Placebo) multiple times assuming the rate of treatment failures among the missing data follows the observed rate of treatment failures in the placebo group.

The following SAS code will be used:

**Note: Treatment Failure will be 1 if a patient had an US or died, 0 if not and ‘.’ if the data is missing (patient withdrew). A dummy baseline variable that consists only 0 will be created. Treatment group will be 1, if the patient received ESL and 2 if the patient received placebo. n will be the number of patients that experienced at least one US until 6 months.**

```
proc mi data=<data> seed=14823 nimpute=&n. out=<out> noint;
  class <Treatment group> <Treatment Failure>;
  var <Baseline Dummy> <Treatment Failure>;
  monotone logistic(<Treatment Failure> /detail);
  mnar model(<Treatment Failure> / modelobs=(trt='2'));
run;
```

The chi-square test as described in 5.5.1 will be applied to each of the imputed datasets. The results will be pooled by Rubin's rule. For the Odds Ratio, the logarithm will be applied before pooling and afterwards the exponential function will be applied:

```
DATA lgsodds_t;
  SET < DATA ODDS>;
  log_or_lr_value=LOG(ODDSRATIO);
  log_or_lr_se=(LOG(UPPERCL)-LOG(LOWERCL)) / (2*1.96);
RUN;
*** Combine transformed estimates;
PROC MIANALYZE DATA=lgsodds_t;
  ODS OUTPUT PARAMETERESTIMATES=mian_lgsodds_t;
  MODELEFFECTS log_or_lr_value;
  STDERR log_or_lr_se;
RUN;
*** Back-transform combined values;
DATA mian_lgsodds_bt; SET mian_lgsodds_t;
  Estimate_back = EXP(ESTIMATE); *Pooled odds ratio;
  LCL_back=Estimate_back*EXP(-1.96*STDERR); *Pooled lower limit;
  UCL_back=Estimate_back*EXP(+1.96*STDERR); *Pooled upper limit;
RUN;
```

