### **5.5.2.3 Time to First Unprovoked Seizure after Randomisation**

For the following analyses, patients will be censored at their last day in the trial.

The time to first US after randomisation will be analysed and presented by means of the Kaplan-Meier estimate (including censored data e.g. withdrawals) after 6, 12 and 18 months for the failure time and corresponding simultaneous CI, a log-rank test (p-value) as well as estimates for 25% percentile, median, and 75% percentile failure time and corresponding CI. The time to first US will be analysed from the day of randomisation.

For this purpose, the following SAS code will be used:

```
ODS OUTPUT Quartiles=quartiles;
ODS OUTPUT ProductLimitEstimates=limit;
ODS OUTPUT HomTests= tests;
PROC LIFETEST DATA=<dataset> METHOD=KM CONFBIAS=EP TIMELIST= 182 365 547;
  TIME <Time to first US>*<Status> (0);
  STRATA <Treatment group> /TEST=LOGRANK;
RUN;
```

The Kaplan-Meier product limit estimate and simultaneous equal precision 95% confidence bands will be graphed.

In case of deaths before the first US, the competing risk of deaths and US will be evaluated exploratively using cause-specific cumulative incidence function and Gray's test for homogeneity in addition.

The following SAS code will be used:

Note: the status will be 0 for censored observations, 1 if US occurred and 2 if the patient died before experiencing an US.

```
ODS OUTPUT GrayTest= graytest;
```

```
PROC LIFETEST DATA=<dataset>;
  TIME <Time to first US or death>*<Status> (0) /eventcode=1;
  STRATA <Treatment group> / order=internal;
RUN;
```

The following statistical outputs will be presented:

Table 15.2.5.1.1 Time to First Unprovoked Seizure after Randomisation– Full Analysis Set

Table 15.2.5.1.2 Time to First Unprovoked Seizure after Randomisation – Per-Protocol Set

The time to first US after randomisation will be presented by estimates for 25% percentile, median, and 75% percentile failure time and corresponding CI; means of the Kaplan-Meier estimate after 6, 12 and 18 months for the failure time and corresponding simultaneous CI (equal precision bands) and the p-value of a log-rank test

Figure 15.2.1.2.1 Time to First Unprovoked Seizure after Randomisation – Full Analysis Set

Figure 15.2.1.2.2 Time to First Unprovoked Seizure after Randomisation – Per-Protocol Set

The Kaplan Meier Product Limit Estimate and simultaneous equal precision 95% confidence bands will be presented for the treatment groups.

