### **5.5.2.8 Overall Survival**

Overall survival (time to death relative to the date of randomisation) will be analysed and presented by means of the Kaplan-Meier estimates (including censored data e.g. withdrawals) after 6 months (Day 182), 12 months (Day 365) and 18 months (Day 547) for the survival rates including pointwise CI, log-rank test as well as estimates for 25% percentile, median, and 75% percentile survival time and corresponding CI.

For this purpose, the following SAS code will be used:

```
ODS OUTPUT Quartiles=quartiles;
ODS OUTPUT ProductLimitEstimates=limit;
ODS OUTPUT HomTests= tests;
PROC LIFETEST DATA=<dataset> METHOD=KM TIMELIST= 182 365 547;
  TIME <Time to death>*<Status> (0);
  STRATA <Treatment group> /TEST=LOGRANK;
RUN;
```

Kaplan-Meier plot for overall survival will be presented.

The following statistical outputs will be presented:

Table 15.2.9.1 Overall Survival – Full Analysis Set

Table 15.2.9.2 Overall Survival – Per Protocol Set

Number and percentage of patients who died and patients censored will be tabulated. The time to death in days will be presented by estimates for 25% percentile, median, and 75% percentile and corresponding CI; means of the Kaplan-Meier estimate after 6, 12 and 18 months for the time to death and corresponding pointwise CI and the p-value of a log-rank test will be presented.

Figure 15.2.5.1 Overall Survival – Full Analysis Set

Figure 15.2.5.2 Overall Survival – Per Protocol Set

The Kaplan-Meier Product Limit Estimate and simultaneous equal precision 95%-Confidence bounds will be presented.

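### For a seizure-free patient who has a re-stroke and then dies, the SAP's re-stroke rule conflicts with its own coding of death, so a known failure may be tabulated as a withdrawal and imputed as a success

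*SAP*

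**What the plan says.** **Classification (SAP 5.5.1).** Order decides: "The first occurring event will be used for this analysis". Then: "If a patient experienced a re-stroke, the patient will be counted as a withdrawal with the date of re-stroke" as the withdrawal date. The same paragraph also says that "deaths before the first US and patients without evaluable assessment of the primary endpoint will be counted as treatment failures", as does the endpoint definition in SAP 2.2.1.

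**Table (SAP 5.5.1).** Death and early withdrawal are separate rows: "Number and percentage of failures (overall, US, death, early withdrawal, missing) and non-failures 6 months after randomisation will be tabulated". SAP 5.5.2.1 uses the same approach at 12 and 18 months.

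**Sensitivity analyses (SAP 5.5.1.1).** The coding note for the multiple imputation reads "Treatment Failure will be 1 if a patient had an US or died, 0 if not and" goes on to make the value missing if the patient withdrew. Missing values in both arms are imputed at the failure rate observed on placebo. The tipping-point analysis sets missing patients to failure or success in all combinations. A third analysis counts only observed US as failures.

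**What a re-stroke is.** The definitions in the protocol synopsis treat an additional stroke within 7 days of the primary stroke as part of one stroke event that does not lead to withdrawal. SAP 5.2.3 also defines re-stroke as a stroke within those 7 days. SAP 5.5.1 gives no time limit and counts any re-stroke as a withdrawal.

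**The concern.** A stroke that kills the patient cannot begin after the death. Under the first-event rule, a seizure-free patient who dies of a re-stroke therefore has the re-stroke first and is a withdrawal. The endpoint definition makes the same patient a failure by death, and the 5.5.1.1 note gives the code 1. No sentence says which rule prevails, so two programmers could code the patient differently and both cite the SAP.

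Two outputs are at stake. The failure breakdown by arm could show too few deaths and too many withdrawals. The imputation and tipping-point analyses, which exist to show how far unknown outcomes could move the result, could treat a known failure as unknown and let it become a success. Recruitment stopped short of the planned size (SAP 2.6), so a few patients may carry weight.

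**Working it through.** **1. The plan's own figures.** The protocol's sample-size section allows for 5% missing data for reasons other than death before the first US. Adjusted rates:
- placebo: 0.26 + 0.05 × (1 − 0.26) = 0.297
- ESL: 0.08 + 0.05 × (1 − 0.08) = 0.126

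Both match the stated 29.7% and 12.6%. The continuity-corrected calculation then gives 100 per arm, with power 80.1% (stated: at least 80%). The planning therefore kept deaths apart from missing data.

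**2. One patient through each rule.** Take a seizure-free patient with a re-stroke counted under 5.5.1 who is known to have died by Day 182.

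| Place | Literal 5.5.1 | Endpoint definition and 5.5.1.1 note |
|---|---|---|
| Primary test | failure | failure |
| Failure breakdown | early withdrawal | death |
| Multiple imputation | missing, drawn at the placebo rate | 1, not imputed |
| Tipping-point grid | failure or success | fixed failure |
| US-only analysis | non-failure | non-failure |

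The conflict is confined to the three middle rows.

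**3. Chance of being imputed as a success.** At the planned placebo rate this is 1 − 0.26 = 0.74 per imputation. With k such deaths, the chance that at least one becomes a success in a given imputation is 1 − 0.26^k: 74%, 93% and 98% for k = 1, 2, 3.

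**4. Effect on the imputed p-value.** Assumptions: 50 per arm (the final size is not given); 13 placebo and 4 ESL failures (26% and 8%), including the fatal re-strokes; no other missing data. Statistic for 13 vs 4: 100 × (|13×46 − 37×4| − 50)² / (50 × 50 × 17 × 83) = 4.54, p = 0.033.

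The k deaths are set to missing and drawn as binomial at the remaining observed placebo rate, r = (13 − k)/(50 − k) if deaths are removed from placebo and 13/50 if they are removed only from ESL. The corrected p is averaged over the draws. For k = 1:
- on placebo: r = 12/49 = 0.245; p is 0.0332 for 13 vs 4 and 0.0562 for 12 vs 4; mean = 0.245 × 0.0332 + 0.755 × 0.0562 = 0.051
- on ESL: r = 0.26; p is 0.0141 for 13 vs 3; mean = 0.26 × 0.0332 + 0.74 × 0.0141 = 0.019

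| Fatal re-strokes | all on placebo | all on ESL | k in each arm |
|---|---|---|---|
| k = 1 | 0.051 | 0.0191 | 0.029 |
| k = 2 | 0.077 | 0.0105 | 0.025 |
| k = 3 | 0.116 | 0.0055 | 0.020 |

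The same method at 100 per arm and 26 vs 8 (p = 0.0014) gives 0.0021, 0.0031, 0.0047 on placebo and 0.0012, 0.0011, 0.0009 with k in each arm. These are averages over draws at a fixed rate, not results pooled by Rubin's rule as the SAP specifies. They show direction and rough size only.

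**5. Tipping-point illustration.** Assume 100 per arm, 11 ESL and 22 placebo observed failures, and 5 withdrawals per arm. With all withdrawals as failures, 16 vs 27 gives p = 0.085. The grid has 6 × 6 = 36 cells, of which 13 have p < 0.05.
- If 3 of the ESL withdrawals are re-stroke deaths held as failures, 3 × 6 = 18 cells remain and 1 is significant.
- If 3 of the placebo withdrawals are, 10 of 18 are.

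With 8 vs 25 observed failures every cell is significant either way, so the effect depends on how close the result is.

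**The case against.** **The 5.5.1.1 note already settles the coding.** It gives 1 to a patient who died, and a programmer who follows it neither imputes that patient nor varies the outcome in the grid. This stands in part: wrong imputation is a possibility, not a certainty. But the note also makes withdrawn patients missing, 5.5.1 makes this patient a withdrawal, and nothing ranks the two.

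**Re-stroke is not clearly defined.** The only definitions given cover 7 days, and the protocol says such a stroke does not cause withdrawal. This stands, and it means the patients caught by 5.5.1 cannot be identified with confidence from the text. It is a second reason to edit the passage.

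**Counting deaths but not seizures after a re-stroke makes ascertainment depend on outcome.** This stands as a small cost. Neither the disposition items in SAP 5.1.1 nor the adverse-event items in 5.6.1 name a death date or vital-status follow-up after withdrawal.

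**The rule was chosen blind.** The revision history places it in Draft 0.5, after the blind data review meeting. That answers any suspicion of a result-driven choice but does not remove the contradiction.

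**Stronger readings that the documents do not support.** A reader might infer that survival is censored at the re-stroke. The rule is not stated in 5.5.2.3 or 5.5.2.8: there, "the status will be 0 for censored observations, 1 if US occurred and 2 if the patient died before experiencing an US", and "Overall survival (time to death relative to the date of randomisation) will be analysed" with no mention of re-stroke. A reader might also infer that these deaths vanish from the report. They still appear in the survival table and the fatal adverse-event outputs, if recorded. Nor does the rule work against one arm: the tables above move both ways.

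**Conclusion.** The point holds as an unresolved conflict between the first-event and re-stroke rules in SAP 5.5.1 and the treatment of death in 2.2.1, 5.5.1 and 5.5.1.1. It affects the death and withdrawal rows at 6, 12 and 18 months, and may affect the 6-month multiple imputation and tipping-point analyses. It does not alter the primary FAS p-value, because both labels count as failure, or the US-only analysis, because neither does.

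The size cannot be fixed from the documents: the number of fatal re-strokes, their split by arm and the final sample size are all absent. On the assumptions in the working, one to three such deaths can carry a p of 0.033 across 0.05 if all are on placebo, or lower it if they are on ESL or evenly split. The direction is therefore unknown. It is worth correcting because a robustness analysis should not vary an outcome that is known, but it does not threaten the primary result.

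**What to change.** Add to SAP 5.5.1, and repeat in the coding note of 5.5.1.1: a death known to have occurred without a prior US by the end of the period (Day 182 or 365, or the end of the 18-month period) is classified as death, with Treatment Failure = 1, whether or not a re-stroke came first; only re-stroke patients whose outcome is unknown are treated as missing. Such deaths are then neither imputed nor varied in the tipping-point grid.

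Because this works only where the death is known, report by arm the number of re-stroke patients and how many have known vital status at the end of each period.

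Reconcile the meaning of re-stroke between the protocol definitions, SAP 5.2.3 and SAP 5.5.1, so that it is clear which patients the withdrawal rule covers.

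No change is needed in 5.5.2.3 or 5.5.2.8. The cost is one sentence in two places, one derivation line and one small table. The primary test and the sample size do not change, and there are slightly fewer values to impute.

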### **5.5.1.1 Sensitivity Analyses**

For the primary analysis, patients withdrawing early during the trial will be considered as non-seizure free (treatment failure). This replacement strategy is defined under the assumption that it cannot be excluded that “missingness” is related to treatment failure and thus not at random. In order to assess the effect of missing data, the following sensitivity analyses will be performed:

The primary analysis will be repeated by imputing the missing values (patient withdrew from study before primary endpoint was reached) in both groups (ESL and Placebo) multiple times assuming the rate of treatment failures among the missing data follows the observed rate of treatment failures in the placebo group.

The following SAS code will be used:

**Note: Treatment Failure will be 1 if a patient had an US or died, 0 if not and ‘.’ if the data is missing (patient withdrew). A dummy baseline variable that consists only 0 will be created. Treatment group will be 1, if the patient received ESL and 2 if the patient received placebo. n will be the number of patients that experienced at least one US until 6 months.**

```
proc mi data=<data> seed=14823 nimpute=&n. out=<out> noint;
  class <Treatment group> <Treatment Failure>;
  var <Baseline Dummy> <Treatment Failure>;
  monotone logistic(<Treatment Failure> /detail);
  mnar model(<Treatment Failure> / modelobs=(trt='2'));
run;
```

The chi-square test as described in 5.5.1 will be applied to each of the imputed datasets. The results will be pooled by Rubin's rule. For the Odds Ratio, the logarithm will be applied before pooling and afterwards the exponential function will be applied:

```
DATA lgsodds_t;
  SET < DATA ODDS>;
  log_or_lr_value=LOG(ODDSRATIO);
  log_or_lr_se=(LOG(UPPERCL)-LOG(LOWERCL)) / (2*1.96);
RUN;
*** Combine transformed estimates;
PROC MIANALYZE DATA=lgsodds_t;
  ODS OUTPUT PARAMETERESTIMATES=mian_lgsodds_t;
  MODELEFFECTS log_or_lr_value;
  STDERR log_or_lr_se;
RUN;
*** Back-transform combined values;
DATA mian_lgsodds_bt; SET mian_lgsodds_t;
  Estimate_back = EXP(ESTIMATE); *Pooled odds ratio;
  LCL_back=Estimate_back*EXP(-1.96*STDERR); *Pooled lower limit;
  UCL_back=Estimate_back*EXP(+1.96*STDERR); *Pooled upper limit;
RUN;
```

A tipping point analysis based on multiple imputation relating the outcome of the primary efficacy analysis to the assumed rate of treatment failure among missing data under ESL and placebo, respectively, will be performed. In the primary analysis, patients with missing data will be classified as 'treatment failure'. By contrast, the tipping point analysis proceeds as follows: Assuming there will be  $N = 1, \dots, n$  missing values for patients in the treatment group and  $M = 1, \dots, m$  missing values for the patients in the placebo group.  $N * M$  datasets will be created, one for each possible combination of imputation for the missing values ('treatment failure' or 'treatment success').

The chi-square test presented in the primary analysis 5.5.1 will be conducted for each of the datasets. Results will be tabulated and p-values will be presented via a heatmap where significant and non-significant p-values will be differently colored. .

Another sensitivity analysis will be conducted based on observed Unprovoked Seizures only as Failure Rate. Death, Withdrawals or patients with missing data will not be counted as a Failure but as a Non-Failure. The primary efficacy analysis will be repeated for this scenario.

The following statistical outputs will be presented:

[Table 15.2.1.3.1 Sensitivity Analysis of Treatment Failure Rate within 6 Months after Randomisation Using Multiple Imputation for Missing Data – Full Analysis Set](#)

[Table 15.2.1.3.2 Sensitivity Analysis of Treatment Failure Rate within 6 Months after Randomisation Using Multiple Imputation for Missing Data – Per-Protocol Set](#)

Degrees of freedom (DF), value and p-value for chi-square test, RD of failing between ESL and Placebo with corresponding 95% continuity-corrected Newcombe CI as well as ESL vs Placebo OR with 95% score confidence interval for the multiple imputed datasets that are combined by Rubin's Rule will be presented.

Table 15.2.1.4.1 Tipping Point Analysis of Treatment Failure Rate within 6 Months after Randomisation – Full Analysis Set

Table 15.2.1.4.2 Tipping Point Analysis of Treatment Failure Rate within 6 Months after Randomisation – Per-Protocol Set

Degrees of freedom (DF), value and p-value for chi-square test, RD of failing between ESL and Placebo with corresponding 95% continuity-corrected Newcombe CI as well as ESL vs Placebo OR with 95% score confidence interval will be presented for all possible combinations of imputed non-failures in ESL and Placebo arm.

Table 15.2.1.5.1 Sensitivity Analysis of Unprovoked Seizures within 6 Months after Randomisation – Full Analysis Set

Table 15.2.1.5.2 Sensitivity Analysis of Unprovoked Seizures within 6 Months after Randomisation – Per-Protocol Set

Table 15.2.1.5.3 Sensitivity Analysis of Unprovoked Seizures within 12 Months after Randomisation – Full Analysis Set

Table 15.2.1.5.4 Sensitivity Analysis of Unprovoked Seizures within 12 Months after Randomisation – Per-Protocol Set

Table 15.2.1.5.5 Sensitivity Analysis of Unprovoked Seizures within 18 Months after Randomisation – Full Analysis Set

Table 15.2.1.5.6 Sensitivity Analysis of Unprovoked Seizures within 18 Months after Randomisation – Per-Protocol Set

Table 15.2.1.5.7 Sensitivity Analysis of Unprovoked Seizures within 18 Months after Randomisation (Subgroup 1) – Full Analysis Set

Table 15.2.1.5.8 Sensitivity Analysis of Unprovoked Seizures within 18 Months after Randomisation (Subgroup 2) – Full Analysis Set

Number and percentage of unprovoked seizures and non-failures 6, 12 or 18 months after randomisation will be tabulated, including degrees of freedom (DF), value and p-value for chi-square test, p-value for Fisher's exact test, RD of failing between ESL and Placebo with corresponding 95% continuity-corrected Newcombe CI as well as ESL vs Placebo OR with 95% score confidence interval.

Figure 15.2.1.1.1 Tipping Point Analysis of Treatment Failure Rate within 6 Months after Randomisation – Full Analysis Set

Figure 15.2.1.1.2 Tipping Point Analysis of Treatment Failure Rate within 6 Months after Randomisation – Per-Protocol Set

Results (p-values) of the tipping point analysis will be presented via heatmap.

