- An expected failure rate (including death before the first US) of 26% under placebo within the first 6 months after stroke.
- An expected failure rate (including death before the first US) of 8% under ESL within the first 6 months after stroke.
- In order to account for a missing data rate of 5% for reasons other than death before the first US, in each treatment arm, the sample size calculated on adjusted failure rates (including missing data) of 29.7% under placebo and 12.6% under ESL, respectively.

Under these assumptions 100 randomised patients per treatment arm will ensure a power of the trial of at least 80% to demonstrate a significantly lower failure rate under ESL compared

to placebo by means of a two-sided chi-square test with continuity correction on a 5%-level of significance.

Assuming that the failure rate in missing observations equals the failure rate with placebo for both treatment groups, the power of the trial is 87%. Based on the expected failure rates without adjustment for missing data, the power of the trial is 89%.

Schedule of trial procedures

Visits	V1a ²	V1b ²	V2 ¹⁵	V3 ¹⁵	V4	V5	V6	V7	V8	EoT ¹²	EDV ³	UNS ¹
Days / Weeks after V1b			+7 days	+37 days	+12 weeks	+26 weeks	+38 weeks	+52 weeks	+64 weeks	+78 weeks		
On-site visit ☺/telephone contact ☎	☺	☺	☺	☺	☎	☺	☎	☺	☎	☺	☺	☺/☎
Day	-3 to -1	1 (within 96 h after stroke)	8±2	38±4	85±10	183±10	267±10	365±10	449±10	547±10		
Initiation procedures												
Informed consent	● ⁹			● ¹⁰							(●) ¹⁴	
Demographics	●											
Medical history	●			● ¹⁰							(●) ¹⁴	
Prior medication	●			● ¹⁰							(●) ¹⁴	
Concomitant medication	●	●	●	●	●	●	●	●	●	●	●	●
SeLECT score/CAVE score ¹¹	● ⁴											
Modified Rankin Scale (mRS)	● ⁴											
Inclusion/exclusion criteria	●	●	● ¹⁰									
Randomisation (1:1)		●										
Medication												
First investigational medicinal product (IMP) administration		●										
Dispense IMP		●									(●)	
IMP accountability				●							● ¹³	(●)
Efficacy												
Issue diary (seizures)	●		●	●		●		●			(●)	
Review and collect diary		● ⁸	●	●		●		●		●	●	(●)
Seizure screening questionnaire	●	●	●	●	●	●	●	●	●	●	●	●
Record seizures (diary/questionnaire) ¹⁶	●	●	●	●	●	●	●	●	●	●	●	●
Barthel Index (BI)	●			●		●		●		●	●	(●)
National Institutes of Health Stroke Scale (NIHSS)	● ⁴		●	●		●		●		●	●	(●)
Patient Health Questionnaire (PHQ-9)	●			●		●		●		●	●	(●)
Electroencephalogram (EEG, optional) ⁵	(● ⁴)									(●)		(●)

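### The multiple-imputation code carries `noint` although only an intercept can deliver the placebo failure rate that the SAP text promises

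*SAP*

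**What the plan says.** SAP section 5.5.1.1 (Sensitivity Analyses) repeats the primary analysis after multiple imputation of patients who withdrew before the primary endpoint was reached. In both arms the imputation is done "assuming the rate of treatment failures among the missing data follows the observed rate of treatment failures in the placebo group". Failure is coded 1 for an unprovoked seizure or death, 0 otherwise, and missing for withdrawal.

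The code given for this has four relevant parts:

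- The covariate: "A dummy baseline variable that consists only 0 will be created".
- The procedure line: "proc mi data=<data> seed=14823 nimpute=&n. out=<out> noint".
- The variable list and model: "var <Baseline Dummy> <Treatment Failure>" and "monotone logistic(<Treatment Failure> /detail". Treatment group is not in the variable list.
- The restriction to placebo patients for fitting: "mnar model(<Treatment Failure> / modelobs=(trt='2".

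The results, pooled by Rubin's rule, go into Table 15.2.1.3.1 (FAS) and Table 15.2.1.3.2 (PPS).

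**The concern.** The text and the code of the same section do not fit together. The logistic imputation model is fitted to placebo patients and has one covariate, which is zero for everyone. A coefficient multiplied by zero adds nothing, so the observed placebo rate can enter the model only through an intercept. The code then prints a keyword whose ordinary meaning is that there is no intercept.

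If the keyword has that effect, the model has no usable parameter, the restriction to placebo patients does nothing, and both tables would report a 50% scenario under a label that says placebo rate. The planned contents of the tables are the test, the risk difference and the odds ratio. They do not include the imputed rate, so a reader could not see the discrepancy. The scenario also matters to the plan: the Protocol's sample size section quotes a power of 87% for the case in which missing patients in both arms fail at the placebo rate.

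**Working it through.** **Inputs from the documents.** Protocol synopsis, sample size estimation: failure 26% under placebo ("An expected failure rate (including death before the first US) of 26% under placebo within the first 6 months after stroke"), 8% under ESL, 5% missing per arm, 100 patients per arm. SAP 5.5.1: "chi-square test with continuity correction on the significance level of 5% (two-sided").

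**The plan's own figures.** With every missing patient a failure, 0.95 × 0.26 + 0.05 = 29.7% and 0.95 × 0.08 + 0.05 = 12.6%. The continuity-corrected sample size is then 100 per arm (power 80.1% by normal approximation, 80.9% by exact enumeration), as stated. With missing patients failing at the placebo rate, ESL becomes 0.95 × 0.08 + 0.05 × 0.26 = 8.9% and placebo stays at 26%. Power is 86.6% exact (85.7% normal), against the stated 87%.

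**What the model returns.** With intercept a, coefficient b and covariate x = 0, logit(p) = a + b × 0 = a.

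- Intercept kept: p is the observed placebo rate. A fit to an assumed 25 failures among 95 observed placebo patients returns 25/95 = 26.3%.
- Intercept suppressed: logit(p) = 0, so p = 50.0% for any b and any data. A fit to the same 95 patients returns 50.0%.

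**Three readings of `noint` on the procedure line.**

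1. It suppresses the intercept: imputation at 50%.
2. It is rejected: the program stops and no table is produced.
3. It is ignored: the intercept stays, the zero dummy is inert, and the placebo rate is imputed as promised.

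**Size if reading 1 applies, equal missingness m.** Expected rate in an arm = (1 − m) × p + m × q, with q = 26% or 50%. Odds ratios are placebo versus ESL. Only m = 5% is from the Protocol; the other values are an assumed range.

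| m per arm | Placebo vs ESL, q = 26% | Placebo vs ESL, q = 50% | Risk difference (both) | OR, q = 26% | OR, q = 50% |
|---|---|---|---|---|---|
| 5% | 26.0% vs 8.9% | 27.2% vs 10.1% | 17.1 points | 3.60 | 3.33 |
| 10% | 26.0% vs 9.8% | 28.4% vs 12.2% | 16.2 points | 3.23 | 2.86 |
| 20% | 26.0% vs 11.6% | 30.8% vs 16.4% | 14.4 points | 2.68 | 2.27 |
| 30% | 26.0% vs 13.4% | 33.2% vs 20.6% | 12.6 points | 2.27 | 1.92 |

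The risk difference does not depend on q, because the term m × q is the same in both arms and cancels. At m = 5%, exact power for a single data set with these rates is 86.6% against 84.7%.

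**Count examples.** Assumed counts, 100 per arm. The log odds ratio is pooled by Rubin's rule over repeated binomial imputation, without parameter uncertainty in the imputed rate. Risk differences are ESL minus placebo. The placebo rate is failures divided by non-missing placebo patients: 25/95 = 26.3%, 24/95 = 25.3% and 20/85 = 23.5%.

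| ESL failures + withdrawn | Placebo failures + withdrawn | RD and p at placebo rate | RD and p at 50% |
|---|---|---|---|
| 8 + 5 | 25 + 5 | −17.0 points, 0.004 | −17.0 points, 0.005 |
| 10 + 15 | 24 + 5 | −11.5 points, 0.06 | −9.0 points, 0.16 |
| 10 + 5 | 20 + 15 | −12.4 points, 0.03 | −15.0 points, 0.015 |

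For the second row, the risk difference at the placebo rate is 10 + 15 × 0.253 − (24 + 5 × 0.253) = −11.5 per 100; at 50% it is 10 + 7.5 − (24 + 2.5) = −9.0. The shift goes against ESL when ESL loses more patients, and in its favour when placebo does.

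**The case against.** A reader might infer that the code as printed imputes at 50%. The documents do not establish that. The keyword stands on the procedure line and not among the options of the logistic statement, which defines the imputation model, and nothing in the SAP shows that it acts on that model. If it is ignored, the stated analysis results. A reader might also blame the all-zero dummy. With an intercept it is harmless, so the suspect item is the single keyword.

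It can further be said that the code is a template with placeholders, that the governing sentence is unambiguous, and that the SAP introduction refers to a validation plan for the programming. The consequence is also contained. The primary analysis counts withdrawals as failures and does not use this code. The tipping-point analysis tabulates combinations of imputed outcomes in both arms, and a further analysis counts observed seizures only. At the planned 5% missing the effect is negligible, and in none of the three count examples does the p-value cross 5%. Those examples use 100 per arm, whereas the SAP reports that recruitment stopped short.

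All of this stands as a limit on the size of the problem. It does not justify the keyword: under no reading does `noint` help to deliver the stated analysis, and the content of the validation plan is not visible.

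**Conclusion.** The SAP promises imputation at the observed placebo rate, and its printed code contains a keyword that defeats this, stops the program, or does nothing. Which of the three applies cannot be settled from the documents, so the 50% figure is conditional on `noint` suppressing the intercept.

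On that condition, the damage is limited to Tables 15.2.1.3.1 and 15.2.1.3.2. With equal missingness the expected risk difference is unchanged and the odds ratio moves towards 1, slightly at the planned 5% (3.60 to 3.33). The risk difference and p-value shift materially only when withdrawals are frequent and unequal, by about 2.5 points in the two unbalanced examples. These sizes rest on the Protocol's 26% and 8% and on assumed withdrawal counts. The primary and tipping-point results are not affected. This is a specification error that should be corrected, not a threat to the trial's main conclusion.

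**What to change.** In the code of SAP section 5.5.1.1, delete `noint`. The model is then intercept-only on the observed placebo patients, and the all-zero dummy can stay. Setting the dummy to 1 and keeping `noint` would be a poorer repair, because it works only if the keyword does suppress the intercept.

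Add one programming check: the mean imputed failure rate, in each arm, agrees within simulation error with the observed placebo failure rate among non-missing patients. Report it as a footnote to the two tables, so that the label can be verified.

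The cost is one word of code and one check line, with no new data. As the SAP is to be final before unblinding, the correction belongs in its text and not in a later program change.
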